### 8.2.7 Sample Size and Power Calculations

Assuming that approximately 135 of the 150 enrolled subjects with recurrent and/or metastatic head and neck cancer will be evaluable for the primary efficacy analysis in the FAS population, the study has approximately 85% power to demonstrate that the ORR is  $>5\%$  with a type I error rate of 1.25% [28]. Success for this hypothesis requires at least 14/135 responses. The null ORR rate of 5% was determined based on a prior randomized trial of methotrexate therapy vs. gefinitib in a second line population in which an ORR of 4% was observed in the methotrexate arm [28].

The proportion of subjects who are PD-L1 strong positive among the 150 subjects enrolled is not known but is estimated to be approximately 20%~30%, then 150 subjects would be expected to provide 30~45 PD-L1 strong positive subjects with recurrent and/or metastatic head and neck cancer will be evaluable for the primary efficacy analysis in the FAS population. [Figure 3](#) shows the power curve ranging about 92% to 99% vs the sample size between 30 and 45, when the ORR $>5\%$  with a type I error rate of 1.25% [28]. Success for this hypothesis requires at least 6 responses out of 30~39 subjects with PD-L1 strongly positive, and at least 7 responses out of 40~45 subjects with PD-L1 strongly positive. The power may increase or decrease depending on the actual number of PD-L1 strong positive subjects who are enrolled in the study ([Figure 3](#)).

[figure not shown]

Figure 3 Power Curve vs Sample Size of PD-L1 Strong Positive Subjects

### **8.2.8 Subgroup Analyses and Effect of Baseline Factors**

All efficacy endpoints will be evaluated by the following categories:

- HPV-positive and HPV-negative subjects
- PD-L1 positive (> 0%) and PD-L1 negative subjects.
- PD-L1 strong positive ( $\geq 50\%$ ) and PD-L1 not strong positive (0 to <50%).

In addition, subgroup analyses of efficacy (ORR, PFS and OS) by the following demographic factors will be performed.

- Baseline ECOG status
- Number of prior therapies

### **8.2.9 Interim Analyses**

No interim analyses are planned in this trial.

### **8.2.10 Compliance (Medication Adherence)**

A day within the study will be considered an On-Therapy day if the subject receives the study medication infusion. The number of Days on Therapy is the total number of days from the first day of study medication to the date of the last dose of study medication.

Summary statistics for the number of Days on Therapy will be provided by treatment group for the FAS population.

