Dosing interruptions are permitted in the case of medical / surgical events or logistical reasons (i.e. elective surgery, unrelated medical events, patient vacation, holidays) not related to study therapy. Patients should be placed back on study therapy within 3 weeks of the scheduled interruption, unless otherwise discussed with the Sponsor. The reason for interruption should be documented in the patient's study record.

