### **5.2.2 Timing of Dose Administration**

Pembrolizumab (MK-3475) should be administered on Day 1 of each three week cycle after all procedures/assessments have been completed as detailed on the Trial Flow Chart (Section 6.0). Trial treatment may be administered up to 3 days before or after the scheduled Day 1 of each cycle due to administrative reasons.

All trial treatments will be administered on an outpatient basis.

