#### **7.1.1.8 Trial Compliance (Medication/Diet/Activity/Other)**

Interruptions from the protocol specified treatment plan for greater than 12 weeks between pembrolizumab (MK-3475) doses require consultation between the investigator and the Sponsor and written documentation of the collaborative decision on subject management.

Administration of trial medication will be witnessed by the investigator and/or trial staff. The total volume of pembrolizumab (MK-3475) infused will be compared to the total volume prepared to determine compliance to each dose of pembrolizumab (MK-3475) administered.

The instructions for preparing and administering pembrolizumab (MK-3475) will be provided in the Pharmacy Manual.

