**AND**

- Experienced an investigator-determined confirmed radiographic disease progression after stopping their initial treatment with pembrolizumab (MK-3475)
- Did not receive any anti-cancer treatment since the last dose of pembrolizumab (MK-3475)
- Has a performance status of 0 or 1 on the ECOG Performance Scale
- Demonstrates adequate organ function as detailed in Section 5.1.2
- Female subject of childbearing potential should have a negative serum or urine pregnancy test within 72 hours prior to receiving retreatment with study medication.
- Female subject of childbearing potential should be willing to use 2 methods of birth control or be surgically sterile, or abstain from heterosexual activity for the course of the study through 120 days after the last dose of study medication (Reference Section 5.7.2). Subjects of child bearing potential are those who have not been surgically sterilized or have been free from menses for > 1 year.
- Male subject should agree to use an adequate method of contraception starting with the first dose of study therapy through 120 days after the last dose of study therapy.
- Does not have a history or current evidence of any condition, therapy, or laboratory abnormality that might interfere with the subject's participation for the full duration of the trial or is not in the best interest of the subject to participate, in the opinion of the treating investigator.

Subjects who restart treatment will be retreated at the same dose frequency as when they last received pembrolizumab (MK-3475). Treatment will be administered for up to one additional year.

Visit requirements are outlined in Section 6.0 – Trial Flow Chart.

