### **8.2.11 Extent of Exposure**

Extent of Exposure for a subject is defined as number of cycles in which the subject receives the study medication infusion. Summary statistics will be provided on Extent of Exposure for APaT population.

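### Section 8.2.10 reports the span from first to last dose as compliance, and that span cannot show adherence to dosing every three weeks

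*Combined protocol and SAP*

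**What the plan says.** Section 8.2.10 (Compliance) has two definitions. The first is that "A day within the study will be considered an On-Therapy day if the subject receives the study medication infusion". The second makes the number of Days on Therapy the "total number of days from the first day of study medication to the date of the last dose of study medication". What is reported is the second: "Summary statistics for the number of Days on Therapy will be provided by treatment group for the FAS population".

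Section 8.2.11 counts the cycles in which a subject received an infusion and reports this in a different population: "Summary statistics will be provided on Extent of Exposure for APaT population".

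On the schedule, Section 5.2.2 states that "Pembrolizumab (MK-3475) should be administered on Day 1 of each three week cycle". Gaps are foreseen. Section 5.2.1.2 has pembrolizumab withheld for listed toxicities and adds that "Dosing interruptions are permitted in the case of medical / surgical events or logistical reasons". Section 7.1.1.8 states that "Interruptions from the protocol specified treatment plan for greater than 12 weeks between pembrolizumab (MK-3475) doses require consultation".

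Section 7.1.5.2.1 allows retreatment after a subject has stopped and then progressed. It calls the retreatment drug study medication and states that "Treatment will be administered for up to one additional year".

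Section 8.0 says that no separate SAP will be issued, so this text is the whole plan on the point.

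**The concern.** A section headed as medication adherence should say how much of the planned dosing was received. A first-to-last-dose span contains no count of doses given or doses due, so two subjects with very different dosing can have the same value.

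The opening sentence adds confusion. It describes a count of infusion days, which is a different quantity and appears nowhere else in the plan. A programmer must either ignore it or guess what it was for.

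The first primary objective is the safety and tolerability of 200 mg every three weeks. A reader of the safety results will want to know how closely subjects kept to that schedule and how often doses were held. The planned compliance summary would not tell them.

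**Working it through.** The documents give no compliance figure to reproduce, so the check applies the definitions to simple dosing calendars. The calendars are illustrations, not forecasts.

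**Inputs.** One infusion every 21 days (Section 5.2.2). First course capped at 24 months from first dose (Section 5.8), taken as 730 days. Earliest stop after complete response at 24 weeks, or 168 days (Section 7.1.5.2.1). Gap lengths and the number of retreatment doses are assumptions.

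**Formulas.** Span = date of last dose − date of first dose (counting both end days adds one). Infusions due within the span = span/21 + 1, rounded down. Ratio = infusions given / infusions due.

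**1. Same end point, doses missed.**
- Every dose given: floor(730/21) + 1 = 35 infusions; span 34 × 21 = 714 days; ratio 35/35 = 1.00.
- Every second dose missed: floor(730/42) + 1 = 18 infusions; span 17 × 42 = 714 days; ratio 18/35 = 0.51.

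The reported measure is identical although about half the doses were not given.

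**2. Same number of infusions, one delayed.**
- Ten on schedule: 9 × 21 = 189 days; ratio 10/10 = 1.00.
- Ten with one 12-week interval: 8 × 21 + 84 = 252 days; infusions due 252/21 + 1 = 13; ratio 10/13 = 0.77.

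The span is 252/189 = 1.33 times as long for the same ten infusions.

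**3. Infusion days against span.** In the complete 24-month course, the opening sentence of Section 8.2.10 gives 35 days and the next gives 714. They are not two ways of computing one number.

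**4. Second Course, read literally.** Suppose a subject stops after complete response at day 168 (nine infusions, 8 × 21) and later receives six retreatment doses (5 × 21 = 105 days).
- Time within the two courses: 168 + 105 = 273 days.
- Reported span with a 90-day gap: 168 + 90 + 105 = 363 days.
- Reported span with a 540-day gap: 168 + 540 + 105 = 813 days.

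The whole excess is time off treatment.

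**5. Does another section fill the hole?** Section 8.2.11 counts cycles received but sets no number of cycles due. Section 7.1.1.8 compares volume infused with volume prepared for each dose given, which cannot show a late or missed dose, and the SAP does not summarise it. Section 8.2.5.2 names no summary of dose holds.

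**The case against.** The strongest reply is that little depends on this summary. The primary safety analysis rests on CTCAE-graded adverse events (Sections 4.2.3.2 and 8.2.3.2). Infusions are witnessed, cycles received are summarised in the APaT, and reasons for discontinuation are displayed (Section 8.2.5.3.1). Only one of the two quantities in Section 8.2.10 is tabulated, so what will be reported is clear. All of this stands, and it makes the point minor. It does not make the span a measure of adherence.

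Four stronger readings are tempting, and the documents do not support them.

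- *A reader might infer that the measure is generally inverted, rising whenever doses are delayed.* That holds only for a fixed number of infusions. Treatment here often ends at an event, or at 24 months counted from first dose, and then a hold leaves the span roughly unchanged. The general fault is insensitivity.
- *A reader might infer that a subject with long holds is less adherent.* Table 3 requires some holds and Section 5.2.1.2 permits others. A subject held under the protocol is following it.
- *A reader might infer a very large Second Course distortion.* A full first course, a 12-month gap and a full second course (18 infusions, 17 × 21 = 357 days) would span 714 + 365 + 357 = 1,436 days, about 47 months. The Trial Summary expects about 36 months for the whole trial, and retreatment requires the study to be open. Nor does Section 8.2.10 say that retreatment doses count; that follows only from its literal wording. Few subjects would be affected: the earlier cohort in Section 4.1.3 had 1 complete response in 56, which would be about 3 in 150 at that rate, plus any who complete 24 months and later progress.
- *A reader might infer that compliance and exposure cannot be combined because one uses the FAS and the other the APaT.* Every FAS subject has had at least one dose (Section 8.2.4.1), so the FAS lies within the APaT and the data can be joined by subject. Only the summary tables differ in denominator; Section 8.2.7 assumes about 135 of 150 in the FAS.

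**Conclusion.** The point holds as a minor descriptive-reporting defect. Followed exactly, Section 8.2.10 yields a summary that cannot show adherence to 200 mg every three weeks, because the span ignores doses due. Its value is about 714 days whether 35 or 18 infusions are given over 24 months, and 189 or 252 days for the same ten infusions. The opening sentence serves no purpose, and the treatment of Second Course doses is unstated.

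The conclusion that the span lacks a denominator rests on the text alone; the day counts rest on the illustrative calendars. The Second Course effect rests on a literal reading and on assumed gap lengths. No efficacy endpoint, alpha, power or success rule is affected.

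**What to change.** In Section 8.2.10:

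- Delete the sentence defining an On-Therapy day.
- Report compliance as infusions received divided by infusions scheduled, at one per 21 days from first dose to treatment discontinuation (relative dose intensity). State whether a dose falling due on the discontinuation date counts.
- Beside it, report the number, length and reason of dose holds, so that holds the protocol requires or permits are not read as non-adherence.
- Present the initial treatment phase and the Second Course separately, in the APaT to match Section 8.2.11.

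Move the first-to-last-dose span to Section 8.2.11 as treatment duration, computed within each phase.

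The cost is a paragraph of SAP text and one variable derived from dosing dates already collected. The adherence figure may look slightly less favourable than a duration would. No clinical rule changes.

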### **8.2.11 Extent of Exposure**

Extent of Exposure for a subject is defined as number of cycles in which the subject receives the study medication infusion. Summary statistics will be provided on Extent of Exposure for APaT population.

## **9.0 LABELING, PACKAGING, STORAGE AND RETURN OF CLINICAL SUPPLIES**

### **9.1 Investigational Product**

The investigator shall take responsibility for and shall take all steps to maintain appropriate records and ensure appropriate supply, storage, handling, distribution and usage of investigational product in accordance with the protocol and any applicable laws and regulations.

Clinical Supplies will be provided by the Sponsor as summarized in [Table 11](#).

Clinical supplies will be packaged to support enrollment and replacement subjects as required. When a replacement subject is required, the Sponsor or designee needs to be contacted prior to dosing the replacement supplies.

Table 11      Product Descriptions

Product Name & Potency	Dosage Form
Pembrolizumab (MK-3475) 100 mg / 4 mL	Solution for Infusion

## **9.2 Packaging and Labeling Information**

Clinical supplies will be affixed with a clinical label in accordance with regulatory requirements.

All supplies will be provided open label. Pembrolizumab will be provided as non-kitted single vials or as single vials in a kit box.

## **9.3 Clinical Supplies Disclosure**

This trial is open-label; therefore, the subject, the trial site personnel, the Sponsor and/or designee are not blinded. Treatment (name, strength or potency) is included in the label text; random code/disclosure envelopes or lists are not provided.

## **9.4 Storage and Handling Requirements**

Clinical supplies must be stored in a secure, limited-access location under the storage conditions specified on the label.

Receipt and dispensing of trial medication must be recorded by an authorized person at the trial site.

Clinical supplies may not be used for any purpose other than that stated in the protocol.

## **9.5 Discard/Destruction>Returns and Reconciliation**

The investigator is responsible for keeping accurate records of the clinical supplies received from the Sponsor or designee, the amount dispensed to and returned by the subjects and the amount remaining at the conclusion of the trial. For all trial sites, the local country Sponsor personnel or designee will provide appropriate documentation that must be completed for drug accountability and return or local discard and destruction if appropriate. Where local discard and destruction is appropriate, the investigator is responsible for ensuring that a local discard/destruction procedure is documented.

## **9.6 Standard Policies**

Trial site personnel will have access to a central electronic randomization system (IVRS/IWRS system) to allocate subjects, to assign treatment to subjects and to manage the distribution of clinical supplies. Each person accessing the IVRS system must be assigned an individual unique PIN. They must use only their assigned PIN to access the system, and they must not share their assigned PIN with anyone.

# **10.0 ADMINISTRATIVE AND REGULATORY DETAILS**

## **10.1 Confidentiality**

### **10.1.1 Confidentiality of Data**

By signing this protocol, the investigator affirms to the Sponsor that information furnished to the investigator by the Sponsor will be maintained in confidence, and such information will be divulged to the institutional review board, ethics review committee (IRB/ERC) or similar or expert committee; affiliated institution and employees, only under an appropriate understanding of confidentiality with such board or committee, affiliated institution and employees. Data generated by this trial will be considered confidential by the investigator, except to the extent that it is included in a publication as provided in the Publications section of this protocol.

### **10.1.2 Confidentiality of Subject Records**

By signing this protocol, the investigator agrees that the Sponsor (or Sponsor representative), IRB/ERC, or regulatory authority representatives may consult and/or copy trial documents in order to verify worksheet/case report form data. By signing the consent form, the subject agrees to this process. If trial documents will be photocopied during the process of verifying worksheet/case report form information, the subject will be identified by unique code only; full names/initials will be masked prior to transmission to the Sponsor.

By signing this protocol, the investigator agrees to treat all subject data used and disclosed in connection with this trial in accordance with all applicable privacy laws, rules and regulations.

### **10.1.3 Confidentiality of Investigator Information**

By signing this protocol, the investigator recognizes that certain personal identifying information with respect to the investigator, and all subinvestigators and trial site personnel, may be used and disclosed for trial management purposes, as part of a regulatory submissions, and as required by law. This information may include:

1. name, address, telephone number and e-mail address;
2. hospital or clinic address and telephone number;
3. curriculum vitae or other summary of qualifications and credentials; and
4. other professional documentation.

Consistent with the purposes described above, this information may be transmitted to the Sponsor, and subsidiaries, affiliates and agents of the Sponsor, in your country and other countries, including countries that do not have laws protecting such information. Additionally, the investigator's name and business contact information may be included when reporting certain serious adverse events to regulatory authorities or to other investigators. By signing this protocol, the investigator expressly consents to these uses and disclosures.

If this is a multicenter trial, in order to facilitate contact between investigators, the Sponsor may share an investigator's name and contact information with other participating investigators upon request.

#### **10.1.4 Confidentiality of IRB/IEC Information**

The Sponsor is required to record the name and address of each IRB/IEC member that reviews and approves this trial. The Sponsor is also required to document that each IRB/IEC meets regulatory and ICH GCP requirements by requesting and maintaining records of the names and qualifications of the IRB/IEC members and to make these records available for regulatory agency review upon request by those agencies.

### **10.2 Compliance with Financial Disclosure Requirements**

Financial Disclosure requirements are outlined in the US Food and Drug Administration Regulations, Financial Disclosure by Clinical Investigators (21 CFR Part 54). It is the Sponsor's responsibility to determine, based on these regulations, whether a request for Financial Disclosure information is required. It is the investigator's/subinvestigator's responsibility to comply with any such request.

The investigator/subinvestigator(s) agree, if requested by the Sponsor in accordance with 21 CFR Part 54, to provide his/her financial interests in and/or arrangements with the Sponsor to allow for the submission of complete and accurate certification and disclosure statements. The investigator/subinvestigator(s) further agree to provide this information on a Certification/Disclosure Form, commonly known as a financial disclosure form, provided by the Sponsor or through a secure password-protected electronic portal provided by the Sponsor. The investigator/subinvestigator(s) also consent to the transmission of this information to the Sponsor in the United States for these purposes. This may involve the transmission of information to countries that do not have laws protecting personal data.

### **10.3 Compliance with Law, Audit and Debarment**

By signing this protocol, the investigator agrees to conduct the trial in an efficient and diligent manner and in conformance with this protocol; generally accepted standards of Good Clinical Practice (e.g., International Conference on Harmonization of Technical Requirements for Registration of Pharmaceuticals for Human Use Good Clinical Practice: Consolidated Guideline and other generally accepted standards of good clinical practice); and all applicable federal, state and local laws, rules and regulations relating to the conduct of the clinical trial.

The Code of Conduct, a collection of goals and considerations that govern the ethical and scientific conduct of clinical investigations sponsored by Merck, is provided in Section 12.1 - Merck Code of Conduct for Clinical Trials.

The investigator also agrees to allow monitoring, audits, IRB/ERC review and regulatory authority inspection of trial-related documents and procedures and provide for direct access to all trial-related source data and documents.

The investigator agrees not to seek reimbursement from subjects, their insurance providers or from government programs for procedures included as part of the trial reimbursed to the investigator by the Sponsor.

The investigator shall prepare and maintain complete and accurate trial documentation in compliance with Good Clinical Practice standards and applicable federal, state and local laws, rules and regulations; and, for each subject participating in the trial, provide all data, and, upon completion or termination of the clinical trial, submit any other reports to the Sponsor as required by this protocol or as otherwise required pursuant to any agreement with the Sponsor.

Trial documentation will be promptly and fully disclosed to the Sponsor by the investigator upon request and also shall be made available at the trial site upon request for inspection, copying, review and audit at reasonable times by representatives of the Sponsor or any regulatory authorities. The investigator agrees to promptly take any reasonable steps that are requested by the Sponsor as a result of an audit to cure deficiencies in the trial documentation and worksheets/case report forms.

The investigator must maintain copies of all documentation and records relating to the conduct of the trial in compliance with all applicable legal and regulatory requirements. This documentation includes, but is not limited to, the protocol, worksheets/case report forms, advertising for subject participation, adverse event reports, subject source data, correspondence with regulatory authorities and IRBs/ERCs, consent forms, investigator's curricula vitae, monitor visit logs, laboratory reference ranges, laboratory certification or quality control procedures and laboratory director curriculum vitae. By signing this protocol, the investigator agrees that documentation shall be retained until at least 2 years after the last approval of a marketing application in an ICH region or until there are no pending or contemplated marketing applications in an ICH region or until at least 2 years have elapsed since the formal discontinuation of clinical development of the investigational product. Because the clinical development and marketing application process is variable, it is anticipated that the retention period can be up to 15 years or longer after protocol database lock. The Sponsor will determine the minimum retention period and notify the investigator when documents may be destroyed. The Sponsor will determine the minimum retention period and upon request, will provide guidance to the investigator when documents no longer need to be retained. The sponsor also recognizes that documents may need to be retained for a longer period if required by local regulatory requirements. All trial documents shall be made available if required by relevant regulatory authorities. The investigator must consult with and obtain written approval by the Sponsor prior to destroying trial and/or subject files.

ICH Good Clinical Practice guidelines recommend that the investigator inform the subject's primary physician about the subject's participation in the trial if the subject has a primary physician and if the subject agrees to the primary physician being informed.

The investigator will promptly inform the Sponsor of any regulatory authority inspection conducted for this trial.

Persons debarred from conducting or working on clinical trials by any court or regulatory authority will not be allowed to conduct or work on this Sponsor's trials. The investigator will immediately disclose in writing to the Sponsor if any person who is involved in conducting the trial is debarred or if any proceeding for debarment is pending or, to the best of the investigator's knowledge, threatened.

In the event the Sponsor prematurely terminates a particular trial site, the Sponsor will promptly notify that trial site's IRB/IEC.

According to European legislation, a Sponsor must designate an overall coordinating investigator for a multi-center trial (including multinational). When more than one trial site is open in an EU country, Merck, as the Sponsor, will designate, per country, a national principal coordinator (Protocol CI), responsible for coordinating the work of the principal investigators at the different trial sites in that Member State, according to national regulations. For a single-center trial, the Protocol CI is the principal investigator. In addition, the Sponsor must designate a principal or coordinating investigator to review the trial report that summarizes the trial results and confirm that, to the best of his/her knowledge, the report accurately describes the conduct and results of the trial [Clinical Study Report (CSR) CI]. The Sponsor may consider one or more factors in the selection of the individual to serve as the Protocol CI and or CSR CI (e.g., availability of the CI during the anticipated review process, thorough understanding of clinical trial methods, appropriate enrollment of subject cohort, timely achievement of trial milestones). The Protocol CI must be a participating trial investigator.

